## SECTION V: RESEARCH PLAN

1. **Statement of Purpose:** State the scientific aim(s) of the study, or the hypotheses to be tested. Alcoholism is a disorder that is mediated by multiple genes and environmental factors. Existing medications like naltrexone and acamprosate are not efficacious in all drinkers. Therefore, we need to develop new and effective strategies to treat alcoholism. Development of medications for this disorder should be based on our understanding of the behavioral and neurochemical mechanisms mediating alcohol reward and drinking. There is extensive preclinical evidence suggesting that glutamatergic circuits are involved in the acute behavioral effects of alcohol as well as in alcohol tolerance and withdrawal. This project will evaluate the effect of an agent that indirectly modulates NMDA-R signaling without directly antagonizing NMDA-Rs on alcohol drinking. Specifically, we will test the influence of Saracatinib, a Src/Fyn protein tyrosine kinase inhibitor that modulates NMDA-R signaling via Fyn inhibition.

**Primary Aim 1:** To evaluate the effects of Saracatinib (125 mg/day) versus placebo on alcohol craving.

*Primary hypothesis 1a:* Saracatinib (125 mg/day) will reduce craving for alcohol after exposure to the priming drink of alcohol, and during the free-choice drinking period, when compared with placebo.

**Primary Aim 2:** To evaluate the effects Saracatinib (125 mg/day) versus placebo on alcohol drinking

*Primary hypothesis 1b:* Saracatinib (125 mg/day) will reduce number of drinks consumed during the free-choice drinking period, when compared with placebo.

**Secondary Aim 1:** To evaluate the effects of Saracatinib (125 mg/day), versus placebo, on alcohol-induced stimulation and sedation during the ADP.

**Secondary Aim 2:** To examine the tolerability of Saracatinib (125 mg/day) in heavy drinkers.

**Exploratory Aims:** To explore predictors of Saracatinib response. The predictors have been selected based on findings from our earlier work and include behavioral outcomes like impulsivity, habit and deficiency in loss-avoidance learning, genetic markers related to alcohol drinking or glutamate and Src/Fyn systems, and neural networks/markers identified using multimodal neuroimaging.

2. **Background:** Describe the background information that led to the plan for this project. Provide references to support the expectation of obtaining useful scientific data.

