**1) Plan for Grading Adverse Events and Attribution of Adverse Events**

Side effects/adverse experiences are collected on standardized forms, using the SAFTEE (Levine and Schooler, 1986). The SAFTEE includes 1) open-ended questions about any changes in physical or health problems, appearance, or activity level, and 2) yes/no questions on a specific list of symptoms (which correspond to anticipated adverse events associated with Saracatinib) for a specified time period. For each symptom reported on the SAFTEE a rater also records the date of onset, severity (minimal, mild, moderate, severe), whether it was drug-related, and action taken. The SAFTEE is administered at baseline, during the inpatient periods, and every other day during the outpatient treatment periods. We will monitor the number of patients experiencing symptoms and the severity of symptoms.

**2) Plans for unanticipated and anticipated serious adverse events reporting to the IRB/HIC, funding agency, and regulatory agency**

**2.a. Definition of Serious Adverse Events:** The FDA's definition of serious adverse events (21 CFR 312) will be used. SAEs include any untoward medical occurrence that at any dose results in death or the immediate risk of death, hospitalization or the prolonging of an existing hospitalization, persistent or significant disability/incapacity, or a congenital anomaly/birth defect (NIH Guide-6/11/99)

**2.b. Plans for reporting serious adverse events:** Adverse events that meet the criteria for a Serious Adverse Event will be reported to the IRB, MAC, and NIAAA within 24 hours by phone and in writing within 1 week.

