**4.b. Frequency of Review of Safety Reports**

Subjects are recruited at a maximum rate of 2 per month; thus, the DSMB will review safety reports two times a year. More frequent meetings will be scheduled if indicated by interim findings.

- d. For multi-site studies for which the Yale PI serves as the lead investigator: N/A
  - i. How will adverse events and unanticipated problems involving risks to subjects or others be reported, reviewed and managed?
  - ii. What provisions are in place for management of interim results? iii. What will the multi-site process be for protocol modifications?

**11. Statistical Considerations:** Describe the statistical analyses that support the study design.

**Power Calculations:** We will recruit up to 90 subjects and randomize 40 subjects to the 125 mg Saracatinib dose and 20 subjects to placebo. We will use the number of drinks consumed at the baseline session (5 or less, 6 or more) and gender as stratification variables in the randomization. 6 drinks is half the total number of drinks they are allowed to drink in the self-administration period and will allow the participant to reach a BAC of 0.07 or higher which is the threshold for heavy drinking. We anticipate that we will obtain complete data on 52 subjects in approximately 2:1 ratio on active vs. placebo. This would give us 80% power to detect large effects of drug ( $d=0.8$  or greater) at two-sided alpha level of 0.05. Such an effect size is considered clinically meaningful and is consistent with our pilot data where we observed large effects of the 125 mg dose (administered over eight days) on alcohol-induced stimulation and feeling intoxicated and feeling good (all  $>0.8$ ) following exposure to a fixed dose of alcohol (0.8 mg/kg) in heavy social drinkers. Randomizing more subjects on active drug will allow us to explore relationships between potential predictors (e.g. gender, smoking status) and outcome in the treatment group. Thus, we will be well powered with our proposed sample to detect clinically relevant effects of Saracatinib.

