**Statistical analyses:** All data will be transcribed onto teleforms, checked for completeness and clarity, and sent to the data manager, [name]. All outcomes will be summarized descriptively and assessed for normality prior to analysis using normal probability plots and Kolmogorov test statistics. Transformations or nonparametric analyses will be performed as necessary. In the mixed models described below, the correlation between repeated measures on an individual will be modeled using random effects and/or structured variance-covariance matrices. The best fitting variance-covariance structure will be determined by information criterion. The mixed effects approach is advantageous in that it is unaffected by randomly missing data and allows greater flexibility in modeling the correlation structure of repeated measures data (Gueorguieva & Krystal 2004). All tests will be two-sided and considered statistically significant at  $\alpha=0.05$ . Significance levels for secondary comparisons will be adjusted for multiple tests using the Bonferroni correction, basing the adjustment on the number of conceptually related statistical tests within each hypothesis.

**Aim 1:** Scores on the Yale Craving Scale will represent the dependent variable in a linear mixed model with treatment (0 or 125 mg Saracatinib) as a between-subjects factor and time (see time points, Table 1) and session (baseline, post-treatment) as within-subject factors. All multilevel interactions will be modeled and interpreted by plotting and comparing least squares means. We anticipate a significant treatment by time by session interaction explained by greater posttreatment reductions in craving with Saracatinib compared to placebo. We will also explore the influence of

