treatment on alcohol craving in response to the alcohol cue exposure just prior to the start of the drinking session using a similar model. In the above models, treatment will be considered as a categorical predictor but linear and quadratic effects of dose will also be tested. **Aim 2:** Total number of drinks consumed during the ADP will be compared among treatment conditions using linear mixed models as above with treatment (0 mg or 125 mg Saracatinib) as a between-subjects factor and session (baseline, post-treatment) as a within-subject explanatory factor. We anticipate a significant treatment by session interaction owing to reduced drinking following Saracatinib treatment, but not placebo. We will also consider change from baseline as the outcome measure and compare the treatment groups using ANOVA.

**Secondary Aim 1:** Alcohol-induced stimulation and sedation during ADP will be evaluated using the same linear mixed models outlined in Specific Aim 1, with BAES subscale scores as the dependent variables.

**Secondary Aim 2:** Adverse events will be recorded and summarized qualitatively by treatment group. Total and severe adverse event frequencies will be compared between groups using chisquare or Fisher's exact test. Similar to what our collaborators, Drs. [name] and [name] observed among AD subjects (see preliminary data), we anticipate AE profiles of the two active Saracatinib groups will be similar to placebo. Vital signs and blood alcohol levels and plasma Saracatinib levels assessed during the ADP will also be evaluated using linear models to examine alcohol-Saracatinib interactions.

**Exploratory Aims:** All measures (e.g., PST, Habit, genetic markers, neural markers) will be evaluated using the same models outlined in Specific Aim 2.

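### Adverse events are compared only by chi-square or Fisher tests; at 40 vs 20 a non-significant result cannot support the expected similarity to placebo, and no risk difference or interval is planned

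*Combined protocol and SAP*

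**What the plan says.** Secondary Aim 2 in Section V.1 is "To examine the tolerability of Saracatinib (125 mg/day) in heavy drinkers". The matching text in Section V.11 has three parts on adverse events:

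- a descriptive part: "Adverse events will be recorded and summarized qualitatively by treatment group";
- an inferential part: "Total and severe adverse event frequencies will be compared between groups using chisquare or Fisher's exact test";
- an expectation drawn from the Alzheimer's disease trial: "we anticipate AE profiles of the two active Saracatinib groups will be similar to placebo".

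The same paragraph adds linear models for vital signs, blood alcohol and plasma drug levels. Section V.11 plans to "randomize 40 subjects to the 125 mg Saracatinib dose and 20 subjects to placebo", and uses a two-sided 0.05 level with a Bonferroni adjustment for secondary comparisons. The safety plan in Section V.10, item 1, says: "We will monitor the number of patients experiencing symptoms and the severity of symptoms". Item 3 there also reports numbers and percentages of subjects.

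The documents give no similarity margin, no interval for a difference in adverse event rates, no power figure for adverse events, and no rule for choosing between the two tests.

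**The concern.** The stated expectation is that the groups will look alike, while the only between-group inference on adverse events is a test for a difference. With 20 placebo participants, such a test returns a large p-value under equal rates and, most of the time, under a sizeable excess as well. A non-significant result therefore separates the two cases poorly, and nothing planned beside it shows how large an excess remains possible.

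The drug is not approved, and here it is combined with alcohol. The experience with that combination described in the protocol is a five-person pilot. The similarity expectation itself comes from a 24-patient trial spread over placebo and three doses. A tolerability statement without its uncertainty could carry over into later work.

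A smaller point is that total frequencies are not defined as participants. The SAFTEE is given repeatedly (daily under Assessments, every other day under the safety plan). Chi-square and Fisher tests need one independent observation per person.

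**Working it through.** **The plan's own figure.** There is none for adverse events. The only power statement is 80% for a standardised difference of 0.8 with 52 completers at about 2:1. At that exact split I get 76.0% (t) or 77.6% (normal approximation). Either way it concerns a mean difference and says nothing about event proportions.

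**Inputs.** Arms of 40 and 20 and two-sided alpha 0.05 are from Section V.11. Bleeding rates are from Section V.8, Healthy Volunteers: 33/187 = 17.6% on drug (doses pooled) and 6/57 = 10.5% on placebo. All other event rates are my assumptions, shown as a range.

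**Power of Fisher's exact test.** Power = sum over all x, y of Bin(x; 40, p1) × Bin(y; 20, p0) × 1[Fisher p ≤ alpha].

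| Placebo | Drug | Fisher, 0.05 | Fisher, 0.025 |
|---|---|---|---|
| 10% | 30% | 37% | 26% |
| 20% | 40% | 28% | 21% |
| 30% | 50% | 25% | 16% |
| 40% | 60% | 23% | 16% |
| 50% | 70% | 29% | 19% |
| 10.5% | 17.6% (bleeding) | 7% | – |

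The 0.025 column applies if total and severe events count as two related tests under the Bonferroni rule, which is an assumption. Uncorrected chi-square at 0.05 does slightly better: 41% (10% vs 30%), 35% (20% vs 40%), 33% (30% vs 50%), 33% (50% vs 70%) and 9% (bleeding). With 35 vs 17, close to the 52 expected completers, Fisher power for a 20-point excess is 22% to 28% at placebo rates of 10%, 20%, 30% and 50%.

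**Excess needed for 80% Fisher power at 40 vs 20.**

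| Placebo rate | Drug rate needed | Excess (points) |
|---|---|---|
| 5% | 36% | 31 |
| 10% | 45% | 35 |
| 20% | 59% | 39 |
| 30% | 70% | 40 |
| 50% | 86% | 36 |

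**What identical observed rates leave open.** The Newcombe interval combines the Wilson limits of each arm. For 8/40 the Wilson limits are 10.5% to 34.8%; for 4/20 they are 8.1% to 41.6%. The difference is 0, so:

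- lower limit = -√[(0.200 - 0.105)² + (0.416 - 0.200)²] = -0.24
- upper limit = +√[(0.348 - 0.200)² + (0.200 - 0.081)²] = +0.19

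Identical rates of 10% give -21 to +15 points; identical rates of 50% give -25 to +25.

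**Non-significant results that point to an excess.**

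- 14/40 vs 2/20 (35% vs 10%): Fisher p = 0.062, Newcombe interval +1 to +42 points. Uncorrected chi-square gives p = 0.039, so the unstated choice of test decides significance here.
- 10/40 vs 1/20 (25% vs 5%): Fisher p = 0.081, chi-square p = 0.059, interval -2 to +36 points. Both tests are non-significant.

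**Severe events.** If none is seen in 40 on drug, the exact two-sided 95% upper limit is 1 - 0.025^(1/40) = 8.8%.

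**The case against.** Four points can be made for the plan, and each limits how far the criticism goes.

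1. A reader might infer that the trial will declare the drug as well tolerated as placebo once the test is non-significant. The documents do not say so. The aim is to examine tolerability, and similarity is an anticipated finding, not a decision rule. What remains is that nothing planned would guard against that reading.
2. A reader might infer that the test usually misses a three- to five-fold excess. That holds only at low placebo rates: 25% vs 5% gives 46%, 20% vs 5% gives 26% and 30% vs 10% gives 37%. At higher rates it fails: 60% vs 20% gives 81% and 50% vs 10% gives 89%. Any event on a repeated symptom checklist may well have a placebo rate above 10%; the documents give none. The absolute excess is the safer scale.
3. The tests are not the only evidence on tolerability. The plan also has the qualitative summary, severity grading, models of vital signs and alcohol levels, repeat laboratory tests and twice-yearly board review. The tests are only the sole between-group inference on adverse events.
4. A reader might infer that repeated events will be tested as if independent. The wording allows this, but the safety plan counts patients, so the participant is the likelier unit.

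Imprecision is unavoidable in a 60-person proof-of-concept trial, and intervals add no power. They do show the imprecision, which the p-value alone hides.

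**Conclusion.** The point holds as a gap in inference, not as a contradiction in the plan. At 40 vs 20, a significant result could contradict the similarity expectation, but a non-significant one cannot support it. Fisher power is 23% to 37% for a 20-point excess at assumed placebo rates of 10% to 50%, and 7% at the protocol's pooled bleeding rates. About 31 to 40 points are needed for 80% power. Even equal observed rates of 20% leave an excess of up to 19 points within the 95% interval.

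These figures assume one binary outcome per participant and analysis of all 60 randomised. Fewer analysed participants or a Bonferroni-adjusted level lowers power further, while chi-square raises it by a few points. The change is worth making because it is nearly free. It touches a secondary aim only and leaves both primary analyses as they are.

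**What to change.** In the Secondary Aim 2 text of Section V.11:

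- Define the outcomes as participants with at least one adverse event and with at least one severe adverse event, in line with items 1 and 3 of the safety plan.
- Make the risk difference (drug minus placebo) with a 95% Newcombe or Miettinen-Nurminen interval the main between-group summary.
- Add the exact upper confidence limit for the severe event rate on drug.
- Keep Fisher's exact test as supportive, and drop the open choice between it and chi-square.
- State that similarity to placebo will not be concluded from a non-significant test.
- Correct the reference to two active groups, since the current design has a single active arm.

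The cost is a few sentences and one or two table columns, with no added participants or visits. The downside is a more cautious statement on tolerability, since the intervals will be wide.

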The current proof-of-concept trial will test the effects of 125 mg dose of Saracatinib versus placebo on alcohol drinking behaviors using the ADP. We have determined that there is a need to focus on the 125 mg dose and that there is no advantage to testing a lower dose (50 mg) of the drug as proposed in the grant. The 50 mg dose is known to be inferior to the 125 mg in terms of Src family target coverage both peripherally and centrally and therefore the pharmacologic effect of the 50 mg dose should not be superior to the 125 mg dose. In addition, this will also allow Astra Zeneca to provide us with the 125 mg and matching placebo over a 3-year period without having to conduct additional stability testing over an extended period of time. Therefore, with the goal of getting this proof of principle trial done in an efficient manner, we will now focus on an adequately powered examination of the 125 mg dose, the dose we believe will be effective based on our preliminary data and knowledge of target engagement. Specifically, in the first three years of the grant, we will recruit 60 subjects and randomize 40 subjects to the 125 mg Saracatinib dose and 20 subjects to placebo. We anticipate a 10% drop out, leaving a final sample of 50 completers.

Thus, 60 non-treatment seeking, heavy drinkers will receive Saracatinib (0 or 125 mg/day), stratified by gender(to achieve 50 completers). Subjects will participate in a baseline ADP, followed by seven days of treatment with the study medication, and then a second ADP when they will take their last dose of study medication. Drinking behavior, alcohol craving and alcohol-induced stimulation/sedation will be measured in each ADP. Adverse events and drinking will be monitored during the treatment period, and at follow up. Potential behavioral predictors of Saracatinib response will be obtained at baseline and post-treatment ADP, and the CTNA core assessment battery will be obtained at baseline.

2. **Research Plan:** Summarize the study design and research procedures using non-technical language that can be readily understood by someone outside the discipline. **Be sure to distinguish between standard of care vs. research procedures when applicable, and include any flowcharts of visits specifying their individual times and lengths.** Describe the setting in which the research will take place.

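### The exploratory aim seeks predictors of Saracatinib response, but no stated analysis includes the treatment-by-predictor term that would test for one

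*Combined protocol and SAP*

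**What the plan says.** The Exploratory Aims in Section V, item 1 open with "To explore predictors of Saracatinib response". The candidates are behavioural measures, genetic markers and "neural networks/markers identified using multimodal neuroimaging".

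In Section V, item 11, the whole analysis text for this aim is "All measures (e.g., PST, Habit, genetic markers, neural markers) will be evaluated using the same models outlined in Specific Aim 2". The Aim 2 model is a linear mixed model for number of drinks, "with treatment (0 mg or 125 mg Saracatinib) as a between-subjects factor and session (baseline, post-treatment) as a within-subject explanatory factor". The only interaction it names is treatment by session, and a change-from-baseline comparison is offered as an alternative. Under Aim 1, after treatment, time and session have been listed, the plan says "All multilevel interactions will be modeled and interpreted by plotting and comparing least squares means".

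The power paragraph in the same item justifies the 2:1 allocation partly because it will "allow us to explore relationships between potential predictors (e.g. gender, smoking status) and outcome in the treatment group".

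Two other places show intent without giving a model. The Assessments list describes impulsivity and habit as baseline predictors of drinking and of response. Section V, item 3 (Genetic Testing) proposes relating medication response on drinking to FYN variants. The Background adds: "Potential behavioral predictors of Saracatinib response will be obtained at baseline and post-treatment ADP". The only scan with a stated time is an optional fMRI at the one-month follow-up (Research Plan).

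**The concern.** A predictor of drug response is a trait across whose levels the drug effect differs. Testing for one needs both arms and a treatment-by-predictor term, and the plan writes no such term. The analyst must therefore choose the model, possibly after seeing the data.

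The one approach to predictors that is described, an association with outcome among those on active drug, does not answer the question. A trait that predicts change in anyone who repeats the drinking session would show the same association. If that were later reported as a marker of Saracatinib response, it could send follow-up work after the wrong trait. The exploratory aim is at stake, not the primary comparisons.

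**Working it through.** **1. How a measure could enter the Aim 2 model.**
- *Measure as outcome.* For behavioural measures taken at both drinking sessions, the treatment-by-session term asks whether the drug changes the measure. That is not prediction. Genotype does not vary by session, so the model cannot be fitted to it. A single one-month scan gives one value, not two.
- *Drinks as outcome, measure added as a factor.* This matches the aim, the Assessments list and the genetics item. It gives a test of prediction only if the interaction of the predictor with treatment and session is included. The Aim 1 sentence on interactions follows a list of treatment, time and session. Extending it to predictors takes two inferences: that the predictor is added, and that the sentence then covers it.

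**2. The plan's own figure.** The plan gives no power or precision for any predictor test. Its only figure is 80% power for a drug effect of d = 0.8 with 52 completers at about 2:1, two-sided 0.05. With 35 and 17 I get 75.6% (t) or 77.2% (normal). That small gap is a separate matter. The inputs used below are 35 active, 17 placebo and two-sided 0.05.

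**3. Active-arm association against interaction.** The correlations are assumptions, since the documents give none. I simulated a predictor with the same correlation r with change in both arms, so there is no moderation, with 20,000 trials per value:

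| r | Significant in active arm | Significant in active, not in placebo | Treatment-by-predictor test significant |
|---|---|---|---|
| 0.2 | 20.9% | 18.5% | 4.9% |
| 0.3 | 41.5% | 32.4% | 5.1% |
| 0.4 | 68.9% | 44.4% | 5.1% |
| 0.5 | 88.5% | 39.7% | 4.7% |

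Repeat runs agreed to within about three percentage points. The third column shows that testing each arm separately does not solve the problem.

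**4. Precision of the interaction test.** For a binary predictor with prevalence f (assumed), in SDs of the change score, SE = sqrt((1/35 + 1/17) / (f(1 − f))), with 52 − 4 = 48 degrees of freedom.
- f = 0.5: SE = sqrt(0.0874/0.25) = 0.591. The 95% interval half-width is 1.19, power for a 0.8 SD interaction is 26%, and 1.69 SD is detectable at 80% power.
- f = 0.3: SE = sqrt(0.0874/0.21) = 0.645. The half-width is 1.30, power is 23%, and 1.84 SD is detectable.
- The Background's 50 completers, taken as 33 and 17, with f = 0.5: SE 0.597, power 26%, 1.71 SD detectable.

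A normal approximation for 52 at exactly 2:1 and f = 0.5 gives 27% and 1.65 SD.

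**5. Same test in either form.** On one simulated complete data set, the predictor-by-treatment-by-session term in the mixed model and the predictor-by-treatment term in the change model gave the same estimate, −0.680 (SE 0.310). Either form the plan allows for Aim 2 will serve.

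**The case against.** The strongest reply is that the plan is incomplete here but not wrong. When the authors swap the outcome they say so: Secondary Aim 1 states that the stimulation and sedation scores become the dependent variables. The exploratory sentence has no such clause, so with the stated aim and the genetics item the natural reading keeps drinks as the outcome. Aim 2 also refers back to the Aim 1 models, so the interaction sentence might carry over. This stands as far as intent goes. It does not supply the missing term. A reader might infer that the plan commits to each measure as the outcome; the text does not support that, as it is only one reading.

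Secondly, the phrase about the treatment group is a rationale for allocation, not an analysis rule. A reader might infer that placebo data will be excluded, or that active-arm associations will be presented as drug-specific. The plan says neither. The percentages in the table are therefore not error rates of the plan. They show what would follow if such associations were reported as drug-specific.

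Thirdly, a reader might conclude that neural markers cannot be baseline predictors. Baseline assessments are referred to a CTNA Clinical Core description that is not in the document, so a pre-treatment scan cannot be ruled out. The point holds only if the one-month scan is the only one.

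Finally, the recommended test has little power. That is true, and it is a reason to report estimates with intervals. It is not a reason to prefer an analysis that answers a different question.

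**Conclusion.** The concern holds as a gap in specification. The stated exploratory aim has no written analysis that tests it, and the within-arm relationship that is described cannot tell prognosis from response. A both-arm interaction can, with data already planned. I am confident of the missing term because no section names it. The sizes shown rest on assumed correlations and prevalences and on 35 and 17 completers.

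A reader might also look for a multiplicity error here. The plan says "Significance levels for secondary comparisons will be adjusted for multiple tests using the Bonferroni correction", which does not clearly reach exploratory tests. Whether to adjust them, or to make no significance claims at all, is a choice for the sponsor and not a defect shown by the documents.

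The primary aims are unaffected and the severity is low.

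**What to change.** In Section V, item 11, replace the Exploratory Aims sentence with wording such as: *Each pre-treatment predictor (baseline behavioural measure, genotype, gender, smoking status) is added to the Aim 2 model for drinks, using both arms, with its interactions with treatment and session. The predictor × treatment × session term, or predictor × treatment in the change-from-baseline model, is the test of response prediction. Estimates are reported with 95% confidence intervals as exploratory.*

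In the power paragraph, state that relationships within the active arm are descriptive.

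For neural markers, make the wording conditional. If the optional one-month fMRI is the only scan, report its markers as post-treatment correlates and amend item 1 to match. That scan follows dosing and the one-week motivational session, either of which may have changed drinking. If a pre-treatment scan exists, state it and use it as the predictor.

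The cost is a few sentences and one extra model per predictor, with no new visit, scan or sample. The drawback is the weak test: with about 26% power for a 0.8 SD interaction at an even split, a null result would not exclude a moderator, and the report should say so.
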